9. RESEARCH DESIGN AND METHODS

The cryoneurolysis procedure will be compared with our current UCSD standard practice.

Study Overview

Day 0

Baseline pain levels and spirometry

Subjects randomized and cryoneurolysis/sham procedure administered
Post-block pain levels and spirometry repeated

Days 1, 2, 7	Pain levels, opioid consumption, sleep disturbances due to pain, and incentive spirometry values collected [day of discharge recorded]
Months 0.5, 1, 1.5 , 2 3, 6, and 12	Pain levels, opioid consumption, sleep disturbances due to pain, and pain interference collected [if subject has spirometer available]

Subjects will be individuals who present to one of the UCSD hospitals with rib fracture(s) and significant pain. The University of Florida will be following the same protocol and the subjects from both institutions will be combined for the analysis. Those who consent to participate in this study will have standard ultrasound-guided intercostal nerve blocks administered with ropivacaine 0.5% (with epinephrine), 3 mL/level of each fracture rib as well as one level above and one level below.

Treatment group assignment (randomization). Subjects will be allocated to one of two possible treatments stratified by treatment center and unilateral vs. bilateral fractures:

1. **active cryoneurolysis (*sham local anesthetic intercostal blocks*)**
2. **sham cryoneurolysis (*active local anesthetic intercostal blocks*)**

Computer-generated randomization lists will be used to create sealed, opaque randomization envelopes with the treatment group assignment enclosed in each envelope labeled with the randomization number.

The specific intercostal nerves targeted will depend on the injury site. The treatment sites will be cleansed with chlorhexidine gluconate and isopropyl alcohol. Using the optimal ultrasound transducer for the specific anatomic location and subject anatomy (linear vs curvilinear array), the target nerves will be identified in a transverse cross-sectional (short axis) view. The intercostal nerve of each fractured rib as well as the level above and below will be treated with the protocol below:

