For subjects at the University of Florida, their anthropomorphic, baseline, procedure, and post-procedure data will be recorded on the same case report form as at the University California San Diego and faxed to the investigators at UC San Diego following the procedure. These faxed documents will remain in electronic form (eFax) on the Principal Investigator's password-protected, encrypted, UCSD-owned MacBook computer. Investigators at UC San Diego will do all of the follow-up data collection by phone for subjects at both treatment centers.

Outcome measurements (end points). Anesthesia providers will perform all measures and assessments, which will include:

1. **Pain:** measured on the 11-point NRS of pain intensity
2. **Opioid consumption**
3. **Pain interference:** measured using the Brief Pain Inventory (which includes the pain scores of #1 above)
4. **Sleep disturbances (#):** due to pain
5. **Pulmonary Mechanics:** measured by the inspired volume on a handheld incentive spirometer based on the American Association of Respiratory Care (AARC) clinical practice guideline.⁷ The best of three measurements will be recorded as the maximum inspired volume.

Statistical Analysis: The primary endpoint is the maximum inspired volume measured by incentive spirometry the day following treatment. There is no accepted minimal clinically-relevant change in incentive spirometry volume. However, the median (IQR) of inspired volume for patients with rib fracture(s) is 1250 (750-1750) mL,⁸ and, ISV<1000 mL is associated with an increased risk of acute respiratory failure.⁸ We will therefore use the difference between 1250 and 1000 (250 mL) as the minimal clinically-relevant difference. However, there is high variability in the reported increase in inspired volume with various regional analgesic interventions such as continuous intercostal nerve blocks⁹ and serratus plane blocks,¹⁰ and we will therefore increase our enrollment to account for an unpredicted increase in variability or non-normal data distribution.

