10. HUMAN SUBJECTS

Inclusion criteria: Adult patients of at least 18 years of age, (1) having a total of 1-6 rib fractures at least 3 cm distal to the costo-transverse joint sustained within the previous 3 days (bilateral fractures are acceptable, but the total of the two sides combined must not exceed 6 fractures); (2) regional anesthetic requested by the admitting service; and, (3) accepting of a cryoneurolysis procedure.

Exclusion criteria: (1) chronic opioid use (daily use within the 2 weeks prior to surgery and duration of use > 4 weeks; of note, any testing for opioid use will not occur as part of the study, but as standard of care); (2) pregnancy; (3) incarceration; (4) inability to communicate with the investigators; (5) morbid obesity (body mass index > 40 kg/m²); (6) possessing any contraindication specific to cryoneurolysis such as a localized infection at the treatment site, cryoglobulinemia, cold urticaria and Reynaud's Syndrome; (7) any patient unable to correctly perform incentive spirometry as this is the primary outcome measure; (8) any patient with any degree of decreased mental capacity as determined by the surgical service; (9) any reason an investigator believes study participation would not be in the best interest of the potential subject; (10) flail chest; (11) chest tube; (12) fracture of the 1st rib on either side; or (13) any moderate or severe pain (NRS>3) unrelated to the rib fracture(s), as best determined by the patient and investigator.

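### Opioid consumption, sleep disturbances and pain interference have no scheduled pre-treatment value, which costs precision and a check of comparability on these secondary outcomes

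*Combined protocol and SAP*

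**What the plan says.** Section 9 (Outcome measurements) lists five outcomes: pain, "Opioid consumption", pain interference, "Sleep disturbances" and inspired volume. Pain interference is "measured using the Brief Pain Inventory (which includes the pain scores of #1 above").

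The Study Overview in the same section sets the schedule:

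- Day 0, before treatment: "Baseline pain levels and spirometry".
- Day 0, after treatment: "Post-block pain levels and spirometry repeated".
- Days 1, 2 and 7: "Pain levels, opioid consumption, sleep disturbances due to pain, and incentive spirometry values collected".
- Month 0.5 onwards: "Pain levels, opioid consumption, sleep disturbances due to pain, and pain interference collected".

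Section 10 admits fractures "sustained within the previous 3 days", and section 11 sets no minimum interval from fracture to participation.

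Under Statistical Analysis (section 9), secondary outcomes go to two-sample t-tests. The repeated-measures model has terms for time, time-by-group, laterality and number of fractures, and no baseline value of the outcome. A baseline covariate appears only in the ANCOVA, which is kept for outcomes with one follow-up time point. Key baseline characteristics are to be compared between groups, but they are not named.

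**The concern.** Two of the five outcomes have a value taken before randomised treatment and three do not. A subject enrolled on the third day after injury may have had several nights of broken sleep and repeated opioid doses; one enrolled within hours may have had neither. Such differences probably carry over into Days 1, 2 and 7, when opioid consumption and sleep are first recorded. With no Day 0 value, the report cannot show whether the groups were alike on these measures, and the analysis cannot use the pre-treatment level to remove between-subject variation. In a trial of 20 evaluable subjects both would be useful.

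The argument is strongest for opioid consumption and sleep in the first week. It is weaker for pain interference, which is first collected two weeks after treatment; the documents give no reason to expect a score taken within three days of injury to predict it well.

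**Working it through.** **Inputs.** From section 9: 10 evaluable subjects per arm, maximum enrolment 30, and for the primary endpoint an SD of 148 mL, a difference of 250 mL and two-sided 5% error. Assumed, because the documents give no figure: a correlation r of 0.3, 0.5 or 0.7 between the Day 0 value and the follow-up value.

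**1. The plan's own figure.** SD = 200/1.35 = 148 mL. With the noncentral t distribution, power is 75.1% at 6 per arm and 82.6% at 7, so the stated 7 per arm is reproduced. The sample size rests on spirometry, which has a Day 0 value, so this point does not change it.

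**2. Chance imbalance.** For a measure in SD units, the difference in baseline means has SD √(2/n).

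- n = 10: √(2/10) = 0.447. P(|difference| > 0.5 SD) = 2 × [1 − Φ(0.5/0.447)] = 0.264, about 26%. Above 0.8 SD it is about 7%.
- n = 15 (all 30 evaluable): √(2/15) = 0.365, and the chance of exceeding 0.5 SD is about 17%.

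These are figures for any one measure.

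**3. Effect on an unadjusted comparison.** A baseline imbalance D shifts the expected follow-up difference by r × D. For D = 0.5 SD the shift is 0.15, 0.25 and 0.35 SD at r = 0.3, 0.5 and 0.7.

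For the false-positive rate given that imbalance, take the critical difference as 2.101 × 0.447 = 0.940 SD (t on 18 degrees of freedom), and the follow-up difference as normal with mean rD and SD 0.447 × √(1 − r²). The approximate rates at r = 0.3, 0.5 and 0.7 are:

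- D = 0.5 SD: 3.7%, 3.9% and 3.2%
- D = 0.8 SD: 5.3%, 8.2% and 11.7%

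**4. What adjustment would gain.** The variance left after adjustment is 1 − r². Estimating the slope in 20 subjects multiplies it by about 1 + 1/(20 − 4) = 1.0625.

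| r | 1 − r² | Gross reduction | × 1.0625 | Net reduction | Detectable difference, 80% power |
|---|---|---|---|---|---|
| none | 1 | – | – | – | 1.32 SD |
| 0.3 | 0.91 | 9% | 0.967 | 3% | 1.31 SD |
| 0.5 | 0.75 | 25% | 0.797 | 20% | 1.19 SD |
| 0.7 | 0.51 | 49% | 0.542 | 46% | 0.98 SD |

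The last column uses 18 degrees of freedom unadjusted and 17 adjusted. It approximates a comparison at one time point with group and baseline in the model.

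**The case against.** The strongest reply is that the trial is randomised. Chance imbalance in an unmeasured variable is part of the sampling error that the t-test and its interval already allow for, and the 26% would apply to any unrecorded variable in any trial of this size. That stands. A reader might infer that an early difference in opioid use or sleep could not be told apart from one present before treatment, or that these comparisons are biased. The documents do not support either reading: over repeated randomisation the unadjusted test keeps its error rate.

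A reader might also infer that nothing about comparability can be seen or adjusted for. That is too strong as well. Baseline pain and spirometry are measured, randomisation is stratified by centre and laterality, and laterality and fracture count are model terms. Section 10 excludes chronic opioid users and patients with moderate or severe pain from other causes. These are partial proxies; none is the outcome's own pre-treatment value.

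Three further points have some force:

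- The schedule is headed as an overview, and section 9 mentions baseline data on a case report form that is not in the documents. The form may hold more. Nothing in the text says so, and the separate listing of pain levels and pain interference means that a baseline pain score cannot be read as a baseline interference score.
- For subjects already in hospital, prior opioid use could be read from the medication record later. That is possible, but it is not planned and would not cover sleep.
- The plan does not contradict itself. Its ANCOVA with a baseline covariate is limited to outcomes with one follow-up, and these three have several. It follows that new Day 0 fields would bring no precision unless the model also changes.

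**Conclusion.** The gap is real and the improvement is optional but cheap. No pre-treatment value is scheduled for three of the five listed outcomes. The consequence is lost precision and no direct way to show comparability on those outcomes; it is not bias. The primary endpoint and the hypotheses in section 6 concern inspired volume and pain, both measured on Day 0, so they are unaffected.

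The size depends on a correlation that the documents do not give. At 0.3 the net gain is negligible; at 0.5 to 0.7 it is worth having. The 26% chance of an imbalance above 0.5 SD assumes 10 per arm and an approximately normal difference in means. The gain would probably be largest in the first week and smaller at the final time point, which is the repeated-measures model's stated parameter of interest.

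**What to change.** At the existing Day 0 assessment, before randomisation:

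- Record opioid consumption and the number of pain-related awakenings over a defined look-back period, together with time since injury. The Brief Pain Inventory interference items can be added as an option, with a weaker case.
- Name these measures among the key baseline characteristics and report them in the baseline table.
- Add each as a baseline covariate in the section 9 model for its own outcome. The t-tests and the repeated-measures model now carry no such term.

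If the measures are not added, the plan should state that these outcomes are analysed without a baseline.

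The cost is a few minutes and several case report form fields per subject, plus one degree of freedom per model. The sample size does not change. The main drawback is that for subjects treated within hours of injury the look-back period covers little post-injury time, so the covariate will be weak for them; this is why time since injury should be recorded with it.

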But, assuming a normal distribution, the interquartile range is approximately 1.35 standard deviations (SDs). Therefore an interquartile range of 250-50 = 200 mL (Hernandez et al. 2019) corresponds to, approximately, an SD of $200/1.35 = 148$ mL. Assuming this SD of 148 mL, a sample size of n=7 per group provides 80% power to detect a group difference of d=250 mL per group with two sided Type 1 Error 5%. To allow for a larger-than-anticipated SD, we will enroll 10 subjects per group with an evaluable primary outcome measure (n=20 for both groups combined). Accounting for drop-outs, we request a maximum enrollment of 30 subjects.

"Continuous data will be summarized with mean, SDs, medians, quartiles, and ranges; and displayed with box-and-whisker plots by group and in aggregate. Key baseline characteristics will be

tested between groups using two-sample t-tests, and summarized with Cohen's D, for continuous measures; and Fisher's Exact test for categorical variables. The primary outcome is maximum incentive spirometry volume (ISV) measured in mL on POD 1. The group difference will be tested using Welch's two-sample test. Secondary outcomes will also be tested with the two-sample t-test. No multiplicity adjustments will be applied for these secondary outcomes. The Wilcoxon signed-rank test will be used as a sensitivity analysis. Secondary analyses will include a Mixed Model of Repeated Measures with fixed-effects for time, time-by-group, unilateral vs bilateral, and the number of fractures. The model will treat time as a categorical variable and will assume a compound symmetric correlation and heterogeneous variance with respect to time. The estimated mean difference between groups at the final scheduled timepoint will be the parameter of interest and will be tested using Kenward-Roger degrees of freedom. Out-comes only measured at baseline and a single follow-up timepoint will be analyses with Analysis of Covariance (ANCOVA). The dependent variable will be change from baseline, and covariates will include group, baseline outcome, unilateral vs bilateral, and the number of fractures. Missing data is not expected due to the short follow-up in this study. However, if missing data issues arise, we will use multiple imputation which is robust to covariate-dependent Missing at Random, and tipping point analyses under various Missing Not at Random assumptions."

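### The sample size rests on an SD of 148 mL that does not fit the primary test; on the plan's own quartiles for inspired volume the SD is about 741 mL, and power for 250 mL with 10 per group is about 11%.

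*Combined protocol and SAP*

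**What the plan says.** Section 9 (Research Design and Methods, Statistical Analysis) defines the endpoint twice, consistently: "The primary endpoint is the maximum inspired volume measured by incentive spirometry the day following treatment" and, in the analysis text, "The primary outcome is maximum incentive spirometry volume (ISV) measured in mL on POD 1". The primary test is unadjusted: "The group difference will be tested using Welch's two-sample test". Section 6, Hypothesis 1a, agrees; volume as a percentage of baseline is a separate, secondary endpoint (Hypothesis 1b).

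The target difference comes from the distribution of raw volume. The plan reports that "the median (IQR) of inspired volume for patients with rib fracture(s) is 1250 (750-1750) mL", notes that volumes below 1000 mL carry a higher risk of respiratory failure, and concludes: "We will therefore use the difference between 1250 and 1000 (250 mL) as the minimal clinically-relevant difference".

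The SD comes from elsewhere. After remarking that "there is high variability in the reported increase in inspired volume" and citing two regional analgesia studies (references 9 and 10), the plan takes quartiles from the second, a serratus plane block study: "Therefore an interquartile range of 250-50 = 200 mL". Dividing by 1.35 gives 148 mL, and the plan states: "Assuming this SD of 148 mL, a sample size of n=7 per group provides 80% power" for a difference of 250 mL at two-sided 5%. It then raises the target to 10 evaluable subjects per group in case the SD is larger, with at most 30 enrolled.

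**The concern.** A two-sample test on raw Day 1 volume needs the between-patient SD of raw Day 1 volume. The plan has a summary of raw volume in this type of patient and uses it to set the 250 mL difference, but not to set the SD. The SD is taken from quartiles of 50 and 250 mL. Those can hardly be raw volumes when the lower quartile of raw volume is given as 750 mL, and the study is cited for increases in volume. The numerator and denominator of the effect size are therefore on different scales.

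This calculation is the only justification for the sample size. If the SD is several times too small, a non-significant primary result would say almost nothing about a 250 mL benefit, yet the protocol would present it as coming from a trial planned with at least 80% power.

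**Working it through.** **Inputs, all from Section 9**
- Difference: δ = 250 mL. Two-sided α = 0.05.
- Conversion: SD = IQR/1.35.
- Plan's SD: (250 − 50)/1.35 = 200/1.35 = 148.1 mL.
- SD from the raw-volume quartiles: (1750 − 750)/1.35 = 1000/1.35 = 740.7 mL. The ratio is 1000/200 = 5.
- Sizes: 7 per group (power claim), 10 per group (evaluable target), 15 per group (all 30 evaluable).

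**Method.** Power comes from the noncentral t distribution with 2n − 2 degrees of freedom and noncentrality λ = δ / (SD·√(2/n)).

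**Step 1: reproduce the plan.** With SD 148.1 and n = 7, λ = 250/(148.1 × 0.5345) = 3.16 and power is 82.6%. With n = 6 power is 75.0%, so 7 is the smallest size that reaches 80%. With n = 10, λ = 3.77 and power is 94.6%. The stated arithmetic holds; only the SD is in question.

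**Step 2: the same calculation with the raw-volume SD.**

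| n per group | λ at SD 740.7 | Power, SD 148.1 | Power, SD 740.7 |
|---|---|---|---|
| 7 | 0.63 | 82.6% | 9.0% |
| 10 | 0.75 | 94.6% | 11.0% |
| 15 | 0.92 | not needed | 14.5% |

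A simulation of the Welch test itself (200,000 replicates, SD 741) gives 8.6%, 10.7% and 14.2% at n = 7, 10 and 15. For 80% power at SD 741, 139 per group are needed (278 evaluable in total). With 10 per group the difference detectable at 80% power is about 980 mL.

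**Step 3: how far the margin reaches.** Solving for the SD at which power for 250 mL is exactly 80% gives about 189 mL at 10 per group and about 236 mL at 15 per group. Going from 7 to 10 therefore covers an SD up to 189/148 = 1.27 times the assumed one.

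**Step 4: SDs between the two figures (assumed values, 10 per group).**

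| SD (mL) | Power for 250 mL | n per group for 80% |
|---|---|---|
| 200 | 75.3% | 12 |
| 300 | 42.2% | 24 |
| 400 | 26.3% | 42 |
| 500 | 18.5% | 64 |
| 600 | 14.3% | 92 |
| 741 | 11.0% | 139 |

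**Step 5: would baseline adjustment help?** Suppose the raw SD is 741 mL at both baseline and Day 1, with correlation ρ. The SD of change is 741·√(2(1 − ρ)). Setting it to 148 gives ρ = 1 − 148²/(2 × 741²) = 0.98. For a baseline-adjusted comparison the residual SD is 741·√(1 − ρ²). Ignoring the degree of freedom spent on baseline, at 10 per group:

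| Assumed ρ | Residual SD (mL) | Power |
|---|---|---|
| 0.7 | 529 | 17.0% |
| 0.8 | 445 | 22.2% |
| 0.9 | 323 | 37.4% |
| 0.95 | 231 | 62.8% |
| 0.98 | 147 | 94.8% |

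The plan states no correlation.

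**The case against.** The best case for the plan has four parts.

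First, 741 mL is not this trial's SD. It comes from a published population, rests on a normal approximation, and may reflect a wider mix of injuries. Section 10 limits entry to 1–6 fractures and excludes flail chest, chest tubes, first-rib fractures, BMI above 40 and inability to perform spirometry, so the Day 1 SD could be smaller. This stands, and 741 mL should be read as conditional. It does not save the power statement, which fails for any SD above about 189 mL.

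Second, the plan does not label the 50–250 mL quartiles as an increase. That reading is an inference from their size and from what the study is cited for. It is an inference, but if they were raw volumes they would contradict the 750–1750 mL quoted in the same section.

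Third, the plan openly acknowledges high variability and adds subjects for it. It deserves credit for that, but the allowance covers a 27% larger SD against a possible fivefold one.

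Fourth, the plan contains analyses that could use baseline. None is the primary test. The mixed model is secondary and targets the final time point. The change-from-baseline ANCOVA is for outcomes with one follow-up, whereas spirometry is repeated on Days 1, 2 and 7.

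In fairness, the plan claims 80% for 7 per group and states no power for 10, so comparisons should be made at equal n.

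**Conclusion.** The concern holds. The fault is an SD that does not match the endpoint and test; the calculation from that SD is right. At equal sample size, power for 250 mL falls from 83% to 9% with 7 per group and from 95% to 11% with 10 per group, if the raw Day 1 SD is the 741 mL implied by the plan's quoted quartiles. That value assumes approximate normality and that the cited population resembles the trial's. A weaker conclusion needs neither assumption about the source: with 10 evaluable per group, 80% power for 250 mL requires a raw Day 1 SD of at most about 189 mL, and nothing in the documents supports an SD of raw volume that small. This must be corrected.

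**What to change.** Rewrite the sample size paragraph on the scale of the primary test. State that, with 10 evaluable subjects per group and an SD of about 741 mL from the cited quartiles, the unadjusted Welch test has about 11% power for 250 mL and 80% power for about 980 mL. Show power over a range of SDs, because the trial's own SD is unknown. Remove the statement that 7 per group gives 80% power for this comparison, and do not carry it over to 10 per group.

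If the sponsor prefers to keep 148 mL, label it as an SD of change, make a baseline-adjusted analysis of Day 1 volume primary, and state and justify the baseline to Day 1 correlation. If the raw SD is 741 mL at both times, that correlation would have to be about 0.98; at 0.9, power with 10 per group is only about 37%. Without support for such a value, this option would replace one unsupported power claim with another.

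If the sample stays as it is, the protocol could describe the trial as a pilot and plan to report the difference with its confidence interval.

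Restating the power costs only protocol wording and a less favourable statement; it requires no extra patients and does not raise the power. Changing the primary analysis would be a protocol amendment, best made before any outcome data are seen by group.

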6. SPECIFIC AIMS

The ultimate objective of the proposed line of research is to determine if cryoanalgesia is an effective treatment for pain associated with rib fractures; and, if this analgesic modality improves pulmonary mechanics measured with incentive spirometry.

Specific Aim 1: To determine if, compared with current and customary analgesia for rib fracture(s), intercostal nerve cryoneurolysis improves maximum inspiratory volume.

Hypothesis 1a: The maximum inspired volume will be significantly *increased* on the day following the procedure [primary endpoint] as well as at other time points following the procedure [secondary end points] with intercostal cryoanalgesia as compared single-injection local anesthetic-based intercostal nerve blocks [measured with an incentive spirometer].

Hypothesis 1b: The maximum inspired volume as a percentage of the baseline will be significantly *increased* on the day following the procedure [secondary endpoint of greatest interest], as well as at other time points following the procedure [secondary end points] with intercostal cryoanalgesia as compared with single-injection local anesthetic-based intercostal nerve blocks [measured with an incentive spirometer].

Specific Aim 2: To determine if, compared with current and customary analgesia, intercostal nerve cryoneurolysis decreases the pain associated with rib fracture(s).

Hypothesis 2a: The severity of rib fracture pain at rest will be significantly decreased within the 12 months following the procedure with intercostal cryoneurolysis as compared with subjects receiving single-injection local anesthetic-based intercostal nerve blocks [measured using the Numeric Rating Scale for pain].

Hypothesis 2b: The severity of rib fracture pain when using the spirometer or coughing will be significantly decreased within the 12 months following the procedure with intercostal cryoneurolysis as compared with subjects receiving single-injection local anesthetic-based intercostal nerve blocks [measured using the Numeric Rating Scale for pain].

Hypothesis 2c: The incidence of chronic pain will be significantly decreased 6 and 12 months following a rib fracture with intercostal cryoneurolysis as compared with subjects receiving single-injection local anesthetic-based intercostal nerve blocks [measured using the Numeric Rating Scale for pain].

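### The primary Welch test of Day 1 volume uses neither baseline volume nor the stratification factors, and no planned analysis gives a baseline-adjusted Day 1 difference in mL

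*Combined protocol and SAP*

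**What the plan says.** All of this is in section 9 of the combined protocol and SAP unless noted.

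- **Primary analysis.** The outcome is maximum inspired volume in mL on the day after treatment. The test is unadjusted: "The group difference will be tested using Welch's two-sample test".
- **Data available.** The Study Overview lists "Baseline pain levels and spirometry" on Day 0, before treatment. Spirometry is repeated after the block and on Days 1, 2 and 7, and later if the subject has a spirometer. Section 10 excludes patients who cannot perform spirometry correctly.
- **Randomization.** Subjects are "allocated to one of two possible treatments stratified by treatment center and unilateral vs. bilateral fractures".
- **ANCOVA.** It is reserved for "Out-comes only measured at baseline and a single follow-up timepoint", and its "covariates will include group, baseline outcome, unilateral vs bilateral, and the number of fractures".
- **Mixed model.** It has "fixed-effects for time, time-by-group, unilateral vs bilateral, and the number of fractures". Its target is stated as follows: "The estimated mean difference between groups at the final scheduled timepoint will be the parameter of interest".
- **Leading secondary endpoint.** Hypothesis 1b in section 6 begins "The maximum inspired volume as a percentage of the baseline will be significantly" and concerns Day 1. Secondary outcomes are tested with an unadjusted two-sample t-test.

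**The concern.** A baseline volume should exist for essentially every subject, and the plan's own ANCOVA accepts adjustment for baseline and laterality in principle. The primary comparison has only 20 evaluable subjects, yet it uses neither these nor center. If baseline predicts Day 1 volume, the variance it explains stays in the error term and the interval is wider than it needs to be.

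There is also a problem of interpretation. With 10 per group, a chance difference in baseline volume could be as large as the 250 mL the trial is meant to detect. No prespecified adjusted estimate would be available to set beside the raw one, and an adjustment chosen after seeing the data would carry little weight.

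**Working it through.** **Inputs from section 9.** Difference 250 mL; two-sided 5%; planning SD 200/1.35 = 148 mL; 10 evaluable subjects per group. Quartiles for rib-fracture patients are 750 and 1750 mL, which under normality give an SD of 1000/1.35 = 741 mL. The correlation ρ between baseline and Day 1 volume is not given, so it is an assumption shown over a range.

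**The plan's own figure.** With 7 per group and SD 148, the noncentrality is 250/(148 × √(2/7)) = 3.16 on 12 degrees of freedom, giving 82.6% power; 6 per group gives 75.1%. The stated 7 is reproduced. At 10 per group, power is 94.6%.

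**Does any planned analysis give a baseline-adjusted Day 1 difference in mL?**

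1. Welch test: no covariates.
2. ANCOVA: limited to outcomes with one follow-up. Spirometry has several, and no scheduled outcome fits the rule.
3. Mixed model: lists neither baseline nor center, and its named contrast is the last visit.
4. Hypothesis 1b: uses baseline, but as a percentage, so it cannot be compared with the 250 mL threshold.

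Center appears in no listed model.

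**Precision.** Adjustment for baseline changes the residual SD to SD × √(1 − ρ²), so the share of variance removed is ρ². For Welch at SD 741, the 95% interval width is about 2 × 2.101 × 741 × √(2/10) = 1392 mL (simulated mean 1390 mL).

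The alternative is an ANCOVA on group, baseline, laterality and center, with 20 − 5 = 15 residual degrees of freedom. It was simulated with 20 subjects, blocks of 4 within strata, 4 of 20 bilateral and 8 of 20 at the second center. Those allocation details are assumptions, and the strata were not prognostic. Each cell had 10,000 trials, except 5,000 for SD 148 at ρ of 0.8 and 0.9.

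| ρ | Variance removed by baseline | Mean CI width, SD 741 (Welch 1390 mL) | Change in width | Power, SD 741 (Welch about 11%) | Power, SD 148 (Welch about 94%) |
|---|---|---|---|---|---|
| 0 | 0% | 1466 mL | 5% wider | 11% | 91% |
| 0.3 | 9% | 1402 mL | 1% wider | 11% | 93.5% |
| 0.5 | 25% | 1270 mL | 9% narrower | 12% | 97% |
| 0.7 | 49% | 1048 mL | 25% narrower | 16% | 99.5% |
| 0.8 | 64% | 881 mL | 37% narrower | 21% | about 100% |
| 0.9 | 81% | 639 mL | 54% narrower | 34% | about 100% |

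A noncentral t calculation with 15 degrees of freedom and variance inflated by 1 + 1/16 for chance baseline imbalance gives 10.5, 11.1, 12.4, 16.0, 20.8 and 34.9% at SD 741, in agreement.

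**Break-even.** Setting (1466/1390) × √(1 − ρ²) = 1 gives ρ² = 1 − (1390/1466)² = 0.10, so ρ is about 0.32.

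**Type I error.** With non-prognostic strata, both analyses reject in about 5% of null trials (Welch 4.9% to 5.2%, ANCOVA 5.0% to 5.2%). If the strata explain 10, 20 or 30% of outcome variance (an assumption) and blocks of 4 are used within strata, Welch rejects in 4.1, 3.2 and 3.0%, while the ANCOVA stays at 4.8% to 5.1%. If allocation is not balanced within strata, Welch rejects in 4.9% throughout. Section 9 states no block size.

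**Chance imbalance.** If the baseline SD is 741 mL, the standard error of the baseline group difference is 741 × √(2/10) = 331 mL. Since 250/331 = 0.75, the difference exceeds 250 mL in either direction in about 45% of trials. At SD 148 the risk is negligible.

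**The case against.** The unadjusted Welch test is a legitimate prespecified primary analysis of a randomized comparison and does not assume equal variances. Section 9 anticipates extra variability and non-normality, so a simple test has some appeal. This stands: no bias or inflation of type I error is claimed. The robustness advantage is small, however. With a 4:1 variance ratio, about 10 per group and ρ of 0.7, null rejection was 5.1% for Welch and 5.6% for the ANCOVA.

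The benefit rests on a correlation the documents do not supply, and below about 0.32 the proposed model is slightly less precise. That also stands. At moderate ρ, power moves little at either SD: 94% to between 97% and 99.5% at 148 mL, and 11% to between 12% and 16% at 741 mL. The gain is mainly in interval width, and it does not settle the conflict between the two SDs, which is a separate sample-size question.

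Adding center and laterality costs about a point of power at SD 741 when they are not prognostic (at ρ = 0.5, 12.7% with baseline alone against 12.2%). The reason to include them is that randomization is stratified on them. The plan's adjusted models also include the number of fractures; whether to add it here is a detail.

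Finally, the mixed model lists no group main effect and could be read as treating baseline as a response. A Day 1 difference in mL would then be estimable. The text does not say so, and the named contrast would still be the last visit.

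**Conclusion.** The concern holds and should be fixed. The primary test uses neither the baseline volume nor the stratification factors, and no baseline-adjusted Day 1 difference in mL is prespecified. This is a loss of efficiency in a valid test.

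Its size depends on the assumed ρ. At SD 741 mL, relative to Welch, the full ANCOVA interval is 5% wider at ρ = 0, about equal at 0.32, 25% narrower at 0.7 and 54% narrower at 0.9. Power at that SD stays at or below 34% for ρ up to 0.9. At the plan's SD of 148 mL, power is above 90% either way. The conservatism of the unadjusted test is conditional: it needs prognostic strata and allocation balanced within them, and the documents establish neither.

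**What to change.** Before unblinding, amend the Statistical Analysis text in section 9 as follows:

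- Make the primary analysis an ANCOVA of Day 1 maximum inspired volume on group, baseline inspired volume, laterality and treatment center. Report the adjusted mean difference in mL with its 95% confidence interval.
- Keep the Welch test as a supportive analysis.
- Add treatment center to the covariates of the mixed model and of the existing ANCOVA.
- Keep percentage of baseline as the planned secondary endpoint.

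The cost is SAP wording, with no new data. The model uses 3 of 18 degrees of freedom. If ρ were 0, the loss would be about 5% in interval width and 0 to 3 points of power.
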